Section 1.2: Revised study plans to have 1 final database lock after the last subject completes the follow-up week 8 visit and a final CSR.

Section 2.3: Removed reference to an addendum report. Specified that dummy treatment groups are used for the draft TLFs for the final CSR prior to DBL, and TLFs for the final CSR are produced unblinded.

Section 2.4: Specified that SAP Version 8 is based on Protocol Version 6.

Section 3.2: In the data sources for endpoints sub-section, updated acute migraine medication days definition. Removed PoM, SM and CGI-c categories.

Section 3.2.3: Specified that Table 3 only includes the endpoints to be assessed. In Table 3, updated sections for exploratory objectives: 1, 2, 6, 7, 10-12, and removed sections for exploratory objectives 3-5 and 13-16.

Section 4.1: Removed text on headache days for migraine analysis set. Removed first month migraine, PK, and OL zavegepant efficacy analysis sets.

Section 4.3: Specified that the randomization strata are based on the actual data and not those assigned in IWRS.

Section 5: Removed language about Type 1 error, testing hierarchy for the primary and secondary endpoints, and exploratory endpoints. Stated that type 1 error is not applicable, and significance of the primary and secondary endpoints will not be evaluated.

Section 6.1.1.1: In Table 4, removed OL zavegepant efficacy and PK by zavegepant treatment group.

Section 6.1.1.2: Added listing of significant protocol deviations.

Section 6.2.1: Removed by-subject listing of subjects excluded from the efficacy analysis.

Section 6.2.3.3: Replaced 'CSR' with 'LSLV'.

Section 6.2.3.4: Replaced 'final' with 'LSLV'. Removed subject disposition table for as-treated treatment group/OL zavegepant dose and overall.

Section 6.2.3.7: Removed Section (treatment in previous studies).

Section 6.2.4: Moved Relevant Protocol Deviations section to new Section 6.2.4.1.

Section 6.2.4.1: Changed analysis set to full in by-subject listing of relevant protocol deviations.

Section 6.2.4.2: Added new section for Significant Protocol Deviations.

Section 6.2.5: Removed text for DB or OL zavegepant safety analysis set. Revised frequency table of randomization stratum to a frequency cross table of randomization stratum from IWRS vs actual data for the full analysis set by treatment group and overall.

Section 6.2.5.1: Updated 2nd bullet to use randomization stratum based on actual data. Removed text for DB or OL zavegepant safety analysis set.

Section 6.2.5.2: Removed table of migraine-related event days per week from OP for first migraine analysis set. Removed sentence on the percentage calculation. Removed reference to sections on headache days per month, migraine days per week and headache days per week.

Section 6.2.5.4: Replaced 'standard of care' with 'acute'.

Section 6.2.6.1: Removed administrative listing of investigational produce batch numbers.

Section 6.2.6.2: Removed DB treatment compliance, OL zavegepant treatment compliance, and ediary usage compliance tables and by-subject listing of treatment compliance. Specified that DB treatment compliance, OL zavegepant treatment compliance, and ediary usage compliance categories are defined for relevant protocol deviations. In sub-sections for DB treatment compliance and OL zavegepant treatment compliance, changed ' $\geq$  80' to '<80'.

Section 6.2.6.3: Removed bullet on migraine standard of care medications. Replaced 'standard of care' with 'acute'.

Section 6.3: Specified that the randomization stratum used in analyses is based on actual data, not from IWRS, and provided the rationale. For the listing of primary and key secondary efficacy endpoints, specified the reasons for exclusion from the migraine analysis set and data methods for presenting endpoints. Removed p-values for all models.

Section 6.3.1: Removed text about data from previous visit to current visit.

Section 6.3.1.3: Removed 'Identity link function, normal distribution'. Removed "subject as a random effect' from the model. Changed 'Repeated measures error structure' to 'Covariance structure for repeated measures accounting for within-subject correlated errors' and modified text describing specification of the covariance structure. Changed 'degrees of freedom method: Kenward-Roger' to Standard error (SE) estimation method: Huber-White "sandwich" (refer to the Core SAP)". Removed the longitudinal plot. Removed sensitivity analyses: jump to reference and tipping point.

Section 6.3.2.1: Replaced 'efficacy dates' with 'efficacy data dates'. In treatment group sub-section, removed  $\geq 75\%$  and 100% percentage reductions.

Section 6.3.2.2: Removed text about data from previous visit to current visit. Specified that acute migraine medication days are prorated. Replaced 'reference time point' with 'efficacy data'.

Removed 'Identity link function, normal distribution'. Changed 'Denominator degrees of freedom method: Kenward-Roger' to 'Standard error (SE) estimation method: Huber-White "sandwich" (refer to the Core SAP)'.

Section 6.3.2.3: Removed text about p-values and hierarchical testing.

Section 6.3.3: Removed Sections 6.3.3.1, 6.3.3.2, 6.3.3.3, 6.3.3.4 and 6.3.3.5.

Section 6.3.3.6: Renumbered to Section 6.3.3.1.

Section 6.3.3.1: Replaced 'reference time point' with 'efficacy data'.

Section 6.3.4: Removed table of plasma zavegepant concentrations along with the text to support this table. Specified that the by-subject plasma zavegepant concentrations will be presented for the DBT efficacy analysis set.

Section 6.4: For On-OL zavegepant for the OL zavegepant safety analysis set, specified to present by OL zavegepant dose and overall. Removed the following: 'OL zavegepant dose and overall, i.e., main presentation', 'Treatment group/OL zavegepant dose and overall, i.e., supplemental presentation'. Removed 'Both presentations are produced'.

Section 6.4.1: Removed 'exposure-adjusted multiple occurrences of unique AEs'.

Section 6.4.1.2: For the AE overview frequency table, removed rows for 'Mild AEs' and 'Moderate AEs', and changed row for 'Severe AEs' to 'Moderate or Severe AEs'.

Section 6.4.1.4: Removed table for exposure-adjusted multiple occurrences of unique AEs along with the calculations.

Section 6.4.1.5: Removed section.

Section 6.4.1.6: Renumbered to Section 6.4.1.5.

New Section 6.4.1.5: Specified to produce the same tables as in Section 6.4.1.4.

Section 6.4.1.7: Removed section.

Section 6.4.1.8: Renumbered to Section 6.4.1.6.

Section 6.4.1.9: Removed section.

Section 6.4.2.1: Removed 'Post-DBT pre-OL zavegepant for the interim safety analysis set' and 'On-DB or OL zavegepant for the DB or OL zavegepant safety analysis set'. Removed tables of laboratory test grade shifts from baseline.

Section 6.4.2.2: Removed bullet: Post-DBT pre-OL zavegepant for the interim safety analysis set. Removed LFT ULN shifts from baseline to worst elevation, exposure-adjusted cumulative LFT elevations, and time to first LFT elevation. Removed LFT plots.

Sections 6.4.2.3 and 6.4.3.1: Removed table of values and changes from DB or OL zavegepant baseline.

Sections 6.4.3.2 and 6.4.4.2: Updated from: 'On-DB or OL zavegepant for the DB or OL zavegepant safety analysis set using DB or OL zavegepant baseline' to: On-OL zavegepant for the OL zavegepant safety analysis set using OL zavegepant baseline'.

Section 6.4.4.1: Removed table of values and changes from DB or OL zavegepant baseline.

Section 6.4.5: Updated from:' On-DB or OL zavegepant for the DB or OL zavegepant safety analysis set' to: On-OL zavegepant for the OL zavegepant safety analysis set'.

Section 6.4.6: Removed bullet: 'Pre-DB or OL zavegepant for the enrolled analysis set treated previously with zavegepant in studies BHV3500-201/301'

Section 6.5: Removed redundant word 'efficacy'. Specified that the randomization stratum used in analyses is based on actual data. Removed the following outcomes research questionnaires and rating scales: PoM, SM, and CGI-c. Removed text about deriving EOT value. Removed p-values for all models.

Section 6.5.1: Removed EOT. Under treatment group comparisons, specified to analyze restrictive role function only. Removed 'Identity link function, normal distribution'. Replaced 'Denominator degrees of freedom method: Kenward-Roger' with 'SE estimation method: See Section 6.3.1.3'. Removed reference to exploratory objective #10.

Section 6.5.2: Specified to analyze total score only. Removed reference to exploratory objective #11.

Sections 6.5.3, 6.5.4, and 6.5.5: Removed sections.

Section 6.6: Specified that only the frequency table of overall COVID-19 impact will be produced. Removed tables for COVID-19 visit impact by visit and missing LFT data impacted by COVID-19 by visit.

Section 7: Replaced 'reference' with 'measurement'. Replaced 'efficacy date' with 'efficacy data date'.

Section 7.2: Removed headache days. Replaced 'efficacy date' with 'efficacy data date'. Removed PoM, SM, and CGI-c.

Section 7.3: Modified analysis visit windows for the Screening and Pre-randomization Visits in Table 5.

Section 8: Specified that all TLFs described in the SAP are produced for the LSLV final CSR.

Section 9.1: Changed 'more than once and assigned' to under. Removed 'for the full analysis set'. Specified how to determine the protocol version to which subjects originally consented. In the medical history section, added 'present at screening'. Added: 'Active medical history status is also identified by the sponsor medical lead or designee from reviewing by-subject listings of medical history and AEs'. Included the definition of 'Present at screening'. Updated text on randomization stratum discrepancies between IWRS and the actual data. Additional checks added under OL zavegepant dosing issues.

Section 9.2.3: Updated definition of acute migraine medication day.

Sections 9.3.1 and 9.3.2: Modified the SAS code by adding the 'empirical' option and removing '/ ddfm=kenwardroger'.

9 Amended version (30-May-2024) based on Protocol Version 6

Signature page: Updated department name for author and approver.

Abbreviations: Removed COVID-19, CYP3A4 and P-gp.

Section 2.4: Specified that SAP Version 9 is based on Protocol Version 6.

Section 3.2: In the intercurrent events subsection, added language for nonstudy acute migraine-specific medication use and nonstudy other medication use to treat headache or aura.

Sections 3.2.1, 3.2.2 and 3.2.3: Added nonstudy acute migraine-specific medication use and nonstudy other medication use to treat headache or aura as intercurrent events for the primary objective, all secondary objectives, and exploratory objectives 1-2 and 6-12.

Sections 3.2.2 and 3.2.3: In summary row for secondary objectives 7-9 and exploratory objectives 8-9, removed "and DB or OL zavegepant".

Section 4.1: Removed "study population" in bullet for the DB or OL zavegepant safety analysis set. Removed the COVID-19 impacted analysis dataset.

Section 6.1.1.1: In table 4, removed row for "OL zavegepant safety, follow-up safety by treatment group/OL zavegepant dose and overall". Removed 'and pretreatment safety' in last sentence.

Section 6.1.1.2: Removed "All listings except administrative listings identify subjects who are impacted by COVID-19." and "and visits impacted by COVID-19 visit impact".

Section 6.2.1: Removed "(excluding COVID-19 impacted)".

Sections 6.2.3 and 6.2.3.1-6.2.3.5: Removed all bullets/categories relating to COVID-19.

Section 6.2.3.4: Moved text for "by OL zavegepant dose and overall" from end of section to first sentence.

Section 6.2.3.5: Moved text for "by as-treated treatment group/OL zavegepant status and overall" from end of section to first sentence.

Section 6.2.3.6: Removed section.

Section 6.2.5: Revised bullet for demographics and other relevant baseline characteristics for the OL zavegepant safety analysis set to use the baseline value (at randomization) and to present by OL zavegepant dose and overall. Removed ", and in COVID-19 analyses by analysis visit (see Section 6.6)."

Section 6.2.5.1: Removed "and calculating age at a reference date" in first sentence. Added "categorical variables" at end of second sentence. Removed last two sentences on OL zavegepant baseline.

Section 6.2.5.2: Corrected typo by replacing small circle with '\geq' for the migraine days per month by pain intensity categories. Removed headache days per month by pain intensity. Specified that categories may be redefined or combined based on the availability of the data.

Section 6.2.6.2: In second bullet of the DBT treatment compliance subsection, added "/OL zavegepant start" after "DB study drug end". In OLE treatment compliance subsection, revised first sentence of the second to last bullet to: "OL zavegepant start date before DB study drug end date." In the eDiary usage compliance subsection, added "/OL zavegepant start" after "DB study drug end".

Section 6.2.6.3: Updated definition of acute migraine medications.

Section 6.4: Removed "Pretreatment for the DBT safety analysis set by treatment group, zavegepant pooled, placebo pooled, and overall".

Section 6.4.1: In Section 6.4.1.2 (AE overviews), for overview tables removed "Moderate or Severe" row, added "SAEs related to Study Drug" row, and removed "Pretreatment for the safety analysis set". Removed Section 6.4.1.3 (Pretreatment AEs) and renumbered other subsections accordingly. Changed "by intensity" to "by worst intensity" in subsections. In new Section 6.4.1.3 (on DBT AEs), removed bullet "AEs of special interest" and sub-bullet "Medication-overuse headache AEs", and removed "by relationship to study drug (related, possibly related, unlikely related, not related, not reported)" from AE related to study drug table.

Section 6.4.2.2: Removed "Pretreatment for the safety analysis set".

Sections 6.4.3.2 and 6.4.4.2: Removed "using OL zavegepant baseline".

Section 6.4.6: Updated criteria to identify participants with non-SAEs leading to discontinuation, select hepatic-related non-SAEs, cardiovascular non-SAEs, and suicidality non-SAEs.

Section 6.6: Removed section.

Section 7.1: Modified the definition of the last contact date to exclude the COVID-19 visit date.

Section 7.2: Removed "and to assess pretreatment safety endpoints". Removed the pre-OL zavegepant and pre-DB or OL zavegepant safety analysis periods. Modified the purpose of the on-treatment safety analysis period.

Section 7.3: Removed "on-DB or OL zavegepant and" from first sentence after table 5. Removed "Zavegepant study days are used to define analysis visit windows in the on-DB or OL zavegepant safety analysis period." and "Analysis visit windows in the on-DB or OL zavegepant safety analysis period are defined analogously to those in the on-treatment safety analysis period."

Section 9.1: Replaced "taken during the DBT Phase" with "start before DB study drug end". Added "/OL zavegepant start" after "DB study drug end". For prohibited non-study medications, removed CYP3A4 and P-gp inducer and inhibitors.

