# 4 ANALYSIS SETS, TREATMENT GROUPS, AND SUBGROUPS

# 4.1 Analysis Sets

The following analysis sets are evaluated and used for presentation and analysis of the data:

- Enrolled: Subjects who sign an informed consent form and are assigned a subject identification number, i.e., nonmissing informed consent date. This analysis set is used mainly to assess study population and in by-subject listings.
- Full: Subjects in the enrolled analysis set who receive a randomized treatment assignment from the IWRS, i.e., nonmissing IWRS randomization date. This analysis set is used mainly to assess study population.
- Safety: Subjects in the enrolled analysis set who take ≥ 1 dose of study drug (zavegepant or placebo), i.e., nonmissing study drug start date. This analysis set is used to assess study population and produce select by-subject listings.
  - O DBT safety: Subjects in the safety analysis set who take ≥ 1 dose of DB study drug (zavegepant or placebo), i.e., nonmissing DB study drug start date. This analysis set is used to assess study population, exposure, and on-DBT safety.
  - OL zavegepant safety: Subjects in the safety analysis set who take ≥ 1 dose of OL zavegepant, i.e., nonmissing OL zavegepant start date. This analysis set is used to assess study population, exposure, and on-OL zavegepant safety.
    - Interim safety: Subjects in the OL zavegepant safety analysis set with OL zavegepant start date DB study drug last date > 7 days. This analysis set is used to assess post-DBT pre-OL zavegepant safety.
  - DB or OL zavegepant safety: Subjects in the safety analysis set who take ≥ 1 dose of DB or OL zavegepant, i.e., nonmissing DB or OL zavegepant start date. This analysis set is used to assess exposure and on-DB or OL zavegepant safety.
  - o Follow-up safety: Subjects in the safety analysis set whose last contact date is in the follow-up safety analysis period. This analysis set is used to assess follow-up safety.
- DBT efficacy: Subjects in the full analysis set who are randomized only once and take ≥ 1 dose of DB study drug (zavegepant or placebo). This analysis set is used mainly to assess DBT outcomes research.

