## 4.2 Treatment Groups

Treatment groups in the DBT Phase are zavegepant 100 mg, zavegepant 200 mg, placebo 100 mg, and placebo 200 mg. OL zavegepant dose groups in the OLE Phase are zavegepant 100 mg and zavegepant 200 mg.

The safety analysis sets are assessed by as-treated treatment group (i.e., actual treatment received), the randomized, full, efficacy, and migraine analysis sets are assessed by as-randomized treatment group, and the enrolled analysis set is assessed overall.

If a subject takes  $\geq 1$  dose of planned randomized DB study drug, then that subject is considered to have as-treated treatment group equal to as-randomized treatment group (see Section 6.2.6.2).

If there are non-randomized subjects who take study drug, then the as-randomized treatment group of "not randomized" is included in the full analysis set augmented with the safety analysis set.

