#### 6.2.4 Protocol Deviations

#### 6.2.4.1 Relevant Protocol Deviations

The frequency table of relevant protocol deviations are provided as the number and percentage of subjects in deviation categories by as-randomized treatment group, zavegepant pooled, placebo pooled, and overall for the full analysis set. Results are shown by deviation type (eligibility, subject management), category, and subcategory in the order specified in Section 9.1. Results for all relevant protocol deviation categories and subcategories are displayed, even those with 0 counts, unless specified otherwise.

A by-subject listing of relevant protocol deviations is provided for the full analysis set. This includes deviation type, category, and subcategory, which are additional sorting variables.

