  - ≤ 5 migraine days, if originally consented to Protocol Version 3 or lower
  - $0 \le 7$  migraine days, if originally consented to Protocol Version 4 or higher
  - $0 \ge 19$  headache days, if originally consented to Protocol Version 3 or lower
  - $\circ$   $\leq$  14 headache days, if originally consented to Protocol Version 4 or higher
  - No headache-free days, if originally consented to Protocol Version 4 or higher. A
    headache-free day is defined as a day of eDiary efficacy data that is not a headache day
    of total pain intensity (see Section 9.2.6).
  - $\circ$  ≤ 23 days of eDiary efficacy data (see Section 9.2.2).

These are assessed during the 28-day OP analysis period (see Section 7.2). Migraine days and headache days are absolute, not prorated to 28 days per month (see Sections 9.2.5 and 9.2.6), and of total pain intensity.

Protocol version for original consent is from the Inclusion/Exclusion CRF.

Relevant subject management protocol deviations include the following categories:

- Randomization stratum discrepancies between IWRS and actual data, defined as any of the following subcategories:
  - o IWRS randomization stratum of yes, but no stable prophylactic migraine medication taken through randomization
  - IWRS randomization stratum of no, but stable prophylactic migraine medication taken through randomization.

See Section 6.2.5.4 for the definition of non-study stable medication through randomization.

- Prophylactic migraine medication usage issue, defined as any of the following subcategories:
  - Prophylactic migraine medication started or stopped from 12 weeks before informed consent to randomization. Defined as informed consent date − 84 days ≤ imputed nonstudy medication start or end date ≤ IWRS randomization date.
  - > 1 prophylactic migraine medication taken on or after informed consent. "> 1" is defined as > 1 unique preferred name.
- DB study drug dosing issue, defined as any of the following subcategories (see Section 6.2.6.2):
  - DB study drug taken but not randomized
  - o More than the required number of DB capsules taken on any 1 day
  - DB capsule count compliance < 80% from DB study drug start to later of last scheduled DBT Phase visit or DB study drug end/OL zavegepant start
  - Incorrect DB study drug taken

- OL zavegepant dosing issue, defined as any of the following subcategories (see Section 6.2.6.2):

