  - OL zavegepant capsule count compliance < 80% from OL zavegepant start to later of last scheduled OLE Phase visit or OL zavegepant end
  - o More than the required number of OL zavegepant capsules taken on any 1 day
  - o OL zavegepant start before DB study drug end
  - OL zavegepant taken but DB study drug never taken
- eDiary usage compliance < 80% from DB study drug start to later of last scheduled DBT Phase visit or DB study drug end/OL zavegepant start (see Section 6.2.6.2)
- Prohibited non-study medications, defined as any of the following subcategories:
  - Atypical antipsychotics, divalproex, valproic acid, or valproate taken on or after informed consent #
  - o Butterbur root or extract taken up to 14 days before randomization or afterward
  - Calcitonin gene-related peptide (CGRP) antagonist biologic or small molecule taken on or after informed consent #
  - o Ergotamine taken on or after informed consent
  - Lamotrigine taken on or after informed consent
  - o Narcotic (barbiturate or opioid) taken up to 2 days before randomization or afterward #

For the subcategories marked with "#", preferred names are displayed alphabetically as additional subcategories. Medications taken up to X days before a reference date or afterward are defined as those with imputed medication start date or imputed end date  $\geq$  reference date -X. Refer to the Core SAP for additional details about prohibited non-study medications.

The IWRS randomization date is the reference date for "randomization". If the IWRS randomization date is missing, then the study drug start date is used.

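### SAP 6.2.4.1 limits the deviation outputs to randomized subjects, so the row for double-blind drug taken without randomization can only print 0 (minor)

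*SAP*

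**What the plan says.** SAP 6.2.4.1 provides the frequency table of relevant deviations "by as-randomized treatment group, zavegepant pooled, placebo pooled, and overall for the full analysis set". On the listing it says: "A by-subject listing of relevant protocol deviations is provided for the full analysis set". The Version 8 entry in the SAP revision history records the change to the listing: "Section 6.2.4.1: Changed analysis set to full in by-subject listing of relevant protocol deviations". On empty rows 6.2.4.1 says: "Results for all relevant protocol deviation categories and subcategories are displayed, even those with 0 counts, unless specified otherwise".

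SAP 4.1 defines the full analysis set as enrolled subjects "who receive a randomized treatment assignment from the IWRS, i.e., nonmissing IWRS randomization date".

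SAP 6.2.6.2 and SAP 9.1 both carry the category "DB study drug taken but not randomized"; in 9.1 it is a subcategory of the double-blind dosing issues.

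SAP 4.2 foresees treated subjects who were not randomized. For them, a not-randomized group "is included in the full analysis set augmented with the safety analysis set". SAP 6.2.1 gives its table of analysis sets a not-randomized column. SAP 6.2.4.1 does not mention the augmented set or such a column.

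SAP 6.2.4.2 also limits the listing of significant deviations to the full analysis set.

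**The concern.** The deviation category describes people who, by definition, lie outside the population of the table that is meant to count them. Because empty rows are printed, a reader of the study report would see an explicit zero and could take it as a checked finding that nobody was dosed without randomization. The row cannot support that conclusion, because it would read the same if there had been cases.

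The row carries more weight since Version 8. According to the revision history for 6.2.6.2, that version removed the compliance tables and the by-subject compliance listing and kept the categories only for relevant deviations. The 6.2.4.1 outputs are now the only ones in this SAP that report the category by name.

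**Working it through.** The plan states no figure here to reproduce. The check is set logic on the SAP's own definitions.

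**Inputs**
- *F*, the population of the table and listing (SAP 6.2.4.1 with 4.1): randomization date in the IWRS not missing.
- *Not randomized* (SAP 6.2.3.1): randomization date in the IWRS missing.
- *D*, the deviation (SAP 6.2.6.2 and 9.1): took double-blind drug and not randomized.
- Display rule (SAP 6.2.4.1): rows with a count of 0 are shown.

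**Step 1.** Membership of F needs a nonmissing date and membership of D needs a missing one. No subject can have both, so F ∩ D is empty.

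**Step 2.** Let k be the true number of non-randomized subjects who took double-blind drug.

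| True k | Row under the full set | Row under full plus safety, with a not-randomized column |
|---|---|---|
| 0 | 0 | 0 |
| 1 | 0 | 1 |
| any k | 0 | k |

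Under the full set the row is correct only when k = 0. The documents do not give k.

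**Step 3.** The two kinds of output fail differently. The table prints a 0; the listings simply omit the subject.

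**Step 4.** Where such a subject would still be seen:
- the analysis-set table, in its not-randomized column, and the analysis-set listing for all enrolled subjects (SAP 6.2.1);
- the enrollment table, in the safety-set count (6.2.2);
- the study drug listing for the safety set (6.2.6.1), since that set requires a dose but not randomization;
- the nonstudy medication listing (6.2.6.3) and the adverse event listing (6.4.1), both for all enrolled subjects.

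Under SAP 6.1.1.2 the by-subject listings are sorted by randomization status unless stated otherwise, and they label subjects outside the full set NRND.

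**Step 5.** Size of the denominator change under the fix. Let m be the number of non-randomized subjects who took any study drug (m ≥ k). The overall denominator goes from N to N + m. With the planned N of about 1440 and m = 1, it becomes 1441, a change of 1/1440 ≈ 0.07%. The number actually randomized is not in the documents.

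**The case against.** The strongest reply is that SAP 4.2 already covers the case. It is a general conditional rule, not tied to one output, and a programmer might apply it to every display of the full set. Table layout also depends on the Core SAP (cited in SAP 6.2) and the mock output document (SAP 6.1.1), neither of which is available, so the printed layout cannot be confirmed. What stands is that the final table might be right. It does not rescue the text: 6.2.4.1 does not call for the augmented set, whereas 6.2.1 names the extra column where it is wanted.

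A second reply is that the event is unlikely. Containers are assigned through the IWRS, and drug is first dispensed at the visit where randomization takes place (Protocol 7.2.1 and 7.2.2; SAP 2.2). This stands, and nothing in the documents suggests that any such case occurred.

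A reader might infer more than the documents support:
- *That such cases would be hidden.* They would not be; the outputs in Step 4 would show them, in the same report as the table that prints 0.
- *That all their other dosing deviations are lost by the choice of set.* Several are undefined for them in any set. The incorrect-drug category is worded for subjects randomized to zavegepant or placebo, the required daily capsule count depends on treatment group, and a stratum discrepancy needs an IWRS stratum. Their concomitant medications, including prohibited ones, remain in the nonstudy medication listing.
- *That the date rule in SAP 9.1 is a further error.* It says: "If the IWRS randomization date is missing, then the study drug start date is used". It has nothing to act on within the full set, but an unused fallback does no harm.

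**Conclusion.** The inconsistency is real and minor. As SAP 6.2.4.1 is written, the row for double-blind drug taken without randomization equals 0 for every k, so it cannot distinguish no cases from some. The relevant and significant deviation listings cannot show such a subject either.

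The consequence stops at deviation reporting. No efficacy analysis set, safety table or confidence interval changes. The conclusion assumes that outputs are programmed from 6.2.4.1 and 6.2.4.2 as they stand, without bringing in the augmented set of SAP 4.2. A wrong number is reported only if k is at least 1; k is unknown and probably zero or small.

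**What to change.** In SAP 6.2.4.1 (table and listing) and 6.2.4.2 (listing), replace the full analysis set with the augmented set of SAP 4.2 (full plus safety). Add a not-randomized column to the 6.2.4.1 table. In that column, mark as not applicable the rows that need a randomized assignment: incorrect double-blind drug, capsule-count compliance and stratum discrepancy. The row for more than the required daily capsules relies on the same group-based requirement and should be treated alike unless a rule is added for it.

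The alternative is to remove the row from the table and report the category separately from the safety analysis set.

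The cost of the first option is a wording change, one extra column and, if any such subjects exist, a slightly larger overall denominator. The set and the column are already named in the SAP; the not-applicable markings would be new.
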